**PI: [name]**

**Co-Investigators: [name], [name]**

**Statistical analysis: [name]**

## **Background**

Hypoglycemia is a common complication of diabetes treatment, particularly when glucose control is intensified (1-3). Until recently, hypoglycemia was regarded as an acceptable "side effect" of glucose lowering therapy, given the benefits of tight glycemic control at reducing microvascular, and to some extent macrovascular, complications of diabetes (2-7). However, studies in the past few years have demonstrated that hypoglycemia is probably a more serious side effect than initially thought (8-11). A major warning as to the potential dangers of hypoglycemia was delivered in the ACCORD study (12), when excess mortality was demonstrated in the intensive glucose arm of the trial, necessitating study termination and fuelling speculation about the role of intensive glucose control in the management of diabetes. The fear of hypoglycemia-induced death in diabetes is not unfounded as there are clear mechanistic pathways to explain this link. Hypoglycemia is associated with repolarisation abnormalities in the heart and increased thrombosis potential as we and others have shown (13-15). Indeed, large scale studies and anecdotal reports have shown associations between acute cardiac events/mortality and hypoglycemic events (11,16-18). Moreover, our preliminary data in Leeds have revealed that severe hypoglycemia, requiring emergency services intervention in 856 patients, is associated with 17.1% mortality within 12 months of the event (unpublished data). This death rate is comparable to diabetes patients sustaining acute cardiac ischemic event in Leeds, which currently stands at 15.8% (19). Also, the mean age of the diabetes cohort was only 61 years, and therefore the high death rate following hypoglycemia is certainly a major cause for concern (for gender and diabetes type distribution, see Figure 1). Moreover, our data showed that in excess of 200 individuals had recurrent severe hypoglycemic events, despite local pathways designed to ensure higher levels of clinical support. Interestingly, of the type 2 diabetes subjects, 28% were not on insulin, being managed with oral hypoglycemic agents (95% treated with sulphonylureas). The degree of documented hypoglycemia in this group was comparable to individuals on insulin therapy with glucose levels at the arrival of ambulance crew of  $1.8 \pm 1.1$  and  $1.9 \pm 0.7$  mmol/l, respectively ( $p > 0.1$ , unpublished data).

**Figure 1.** Type of diabetes and gender distribution of individuals with severe hypoglycemia requiring emergency services intervention in Leeds (1307 events).

It is unclear at this stage whether the observed increased mortality following severe hypoglycemia is directly related to low plasma glucose or whether severe hypoglycemia is more likely to occur in individuals with terminal clinical conditions (20), which may be due, for example, to weight loss and/or decreased appetite. Naturally, this needs to be clarified as it has important clinical implications for the treatment of these individuals.

Studies on the occurrence of severe hypoglycemia in the community have been both limited and incomplete. In particular, the predictors of severe hypoglycemia

in the community have not been fully evaluated, which is partly due to the inadequate methodologies used or the inappropriate statistical methods employed (21-23). A recent retrospective observational study, conducted in Australia, has shown that duration of insulin treatment, renal factors and diabetic neuropathy are some of the predictors of severe hypoglycemia (24). Furthermore, this study has demonstrated that high HbA1c levels are not necessarily associated with lower risk of severe hypoglycaemia. It remains unclear, however, whether infrequent blood glucose testing and inadequate clinical support has a role in increasing the risk of severe hypoglycemia, whereas the effect of co-morbidities requires further clarification. For example, any clinical condition that is associated with weight loss or reduced appetite may be contributing to hypoglycemia. Another example is excess alcohol intake, which may also result in frequent and severe hypoglycemia (more details are provided below).

### **Hypothesis**

Inadequate education, infrequent glucose testing and clinical co-morbidities in subjects with diabetes are associated with severe hypoglycemic episodes. Therefore, structured diabetes specialist input with regular glucose testing is important to reduce the risk of severe hypoglycemia.

[figure not shown]
### **Aims**

The proposed work is divided into two parts through an observational and an interventional study.

1. Observational study: characterise individuals with severe hypoglycemia.
2. Interventional preliminary study: investigate the effect of regular glucose monitoring and specialist nurse input into a) future hypoglycemic events, b) confidence with diabetes management/quality of life and c) clinical outcome.

[figure not shown]
### **Plan of investigation**

We have already developed a pathway for ambulance services to report cases of severe hypoglycemia in Leeds requiring their intervention (Figure 2).

**Figure 2.** A summary of the current severe hypoglycemia pathway in Leeds. YAS: Yorkshire Ambulance Services, DNS: Diabetes Nurse Specialist, GP: General Practitioner.

We will continue to follow this pathway but will have a dedicated nurse to deal with the patients and will extend the study to include Sheffield. Inclusion of Sheffield will help to boost the number of patients enrolled and will clarify any potential regional variability. The research nurse will be experienced in managing individuals with diabetes and will be conducting both parts of the study, under the supervision of the principal investigator. The proposed study is summarised in Figure 3 and further detailed below.

**Figure 3.** Summary of study design, including both observational and interventional parts. Intensive nursing support and standard clinical care are explained in more detail below.

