### **Interventional study**

We will conduct a preliminary interventional study, where patients will be randomised to either intensive monitoring/treatment modification, where patients are closely followed up by the research nurse, or conventional therapy following local protocols. Individuals in the interventional part of the study will be:

[figure not shown]
- i) Regularly contacted by the research nurse as detailed below.
- ii) Encouraged to check their glucose levels as appropriate, at least twice a day or more frequently as necessary.
- iii) Special leaflets regarding different aspects of diabetes will be given to patients and will be discussed. These will include leaflets for alcohol, exercise, Carbohydrate counting and awareness as appropriate (please see below).
- iv) Patients will have a dedicated phone number that they can ring for urgent advice.
- v) There will be a dedicated email line set up to answer less urgent queries and help with patient support. An email system is already set up in Leeds by the PI, and patients using this service experienced significant improvement in diabetes control (data not shown).

The research nurse will make every attempt to establish the cause of severe hypoglycemia by taking a detailed medical history in order to clarify clinical comorbidities and assess social circumstances including alcohol intake, patient independence and help provided by carers. The nurse will also document current medications with special attention to dose and frequency of hypoglycemic agents, including insulin. Routine blood tests to assess overall glycemic control, renal and liver function will be performed, which may further help to shed light on the cause of low blood glucose. Hypoglycemic treatment may be changed in cases of concern but only after review by the PI, and the medical team in charge of the patient will be informed. For example, a sulphonylurea may be stopped or replaced if deemed inappropriate for the patient and insulin regimens/doses may also be altered. Follow up of patients after changes to medical therapy are detailed below but some may have more frequent contact with the nurse as per clinical need. The nurse employed will have extensive experience in the management of diabetes and will have the necessary knowledge to adjust doses/mixtures/intervals of insulin as appropriate, with adequate support provided by the PI in difficult clinical scenarios. Other diabetes disciplines, such

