as dietitian support may be sought if the research nurse and/or PI find this to be necessary. In cases of newly diagnosed (or suspected) clinical conditions, referrals to an appropriate specialty will be made after review by the PI. If social circumstances are found to be inappropriate, for example in the case of older individuals not managing on their own, the physician in charge of the patient will be informed and steps will be taken to provide support according to the need of each individual.

In summary, the research nurse will concentrate on establishing the cause of the severe hypoglycemic episode and together with the PI will alter treatment, involve other diabetes/non-diabetes disciplines as appropriate and introduce changes to social support as required.

The research nurse will contact the patient weekly for the first month, every two weeks for the following month followed by contact at months 3, 6 and 12. Face to face contact with the patient will be arranged at enrolment, 1, 3 and 12 months. Patient will be asked to fill in the questionnaire at enrolment and end of 3rd month, with selected patients asked to complete the form again at 12 months (explained in Figure 4). Blood tests will be arranged as detailed above. In the standard arm, patient will be contacted only once as per current arrangement and subsequent treatment left to the discretion of the attending physician (summarised in Figure 4).

**Figure 4.** Summary of the preliminary interventional part of the study. U&Es: urea and electrolytes, LFTs: liver function tests, UACR: urinary albumin/creatinine ratio, MACE: major adverse cardiovascular events, m:

month, d: day. Questionnaire will be done at enrolment and 3 months in both groups. If a significant difference exists between the two time points in the same patient, the questionnaire will be repeated at 12 months. Clinical outcome at 12 months will also include frequency of hypoglycemia, analysed separately.

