### **Statistical analysis**

The observational part of the study will collect various data and will be the basis for future studies. Power calculations were based on the interventional study. Given our current data showing a death rate in excess of 17% within one year of hypoglycemia, we calculated that 200 individuals are needed in each of the study arms to detect a drop in mortality to 10% in intensively monitored patients (at  $p=0.05$ ). Between group analysis will be done using unpaired  $t$ -test for normally distributed data and the non-parametric Mann-Whitney test will be used for data that are not normally distributed. For categorical data, 2X2 contingency tables will be used and multiple regression analysis will be performed to determine potential causes of hypoglycemia.

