**1. Insulin users**

In all insulin users, hypoglycemia with insulin use will be discussed together with the effects of exercise and alcohol on blood glucose (see appendix 3a). Also, hypoglycaemia unawareness will be discussed in detail. More specific education will be given according to type of insulin regime

- a. Basal bolus and complex insulin regimes

Teach CHO counting (structured education with dietitian already in place)

- b. BD or od insulin

Discuss CHO awareness (see appendix 3a)

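### Sheffield is added partly to examine regional differences, but nothing in the visible randomisation or analysis plan uses city

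*Combined protocol and SAP*

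**What the plan says.** - **Purpose.** Plan of investigation, on Sheffield: "Inclusion of Sheffield will help to boost the number of patients enrolled and will clarify any potential regional variability". The same section describes what already exists in Leeds: "We have already developed a pathway for ambulance services to report cases of severe hypoglycemia in Leeds requiring their intervention".
- **Comparator.** Interventional study: controls receive "conventional therapy following local protocols". In the standard arm the "patient will be contacted only once as per current arrangement and subsequent treatment left to the discretion of the attending physician". Sheffield's usual care is not described.
- **Email.** A dedicated email line is one of the five listed components of the intervention. The same item adds: "An email system is already set up in Leeds by the PI, and patients using this service experienced significant improvement in diabetes control".
- **Randomisation.** Patients are randomised to two arms. The visible text names no stratification factor. The design figures are not available in the text reviewed.
- **Analysis.** The Statistical analysis section is a single paragraph. "Between group analysis will be done using unpaired" t-tests, or Mann-Whitney tests where data are not normal, with 2×2 tables for categorical data. A multiple regression on what may cause hypoglycemia is also planned, without listed covariates. City is not mentioned.
- **Data.** Address is among the demographic items in the Observational study section, so city can be derived.

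**The concern.** A stated reason for adding a city should lead to an analysis, and here it leads to none. If city is examined only after the data are in, the choice of outcome, model and summary is open, and a regional statement made on that basis carries little weight.

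City also matters more than usual because the comparator is defined by local practice. If usual care were richer in one city, the contrast between arms would be smaller there. A small pooled effect would then be hard to read without at least a description by city. Whether care does differ is unknown from the documents, which is itself a reason to plan the description rather than leave it out.

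**Working it through.** **Inputs.** 12-month mortality of 17% in controls and 10% in the intensive arm, 200 per arm, p = 0.05 (Statistical analysis). The 17% rests on Leeds data only (Background gives 17.1%). The city split is not stated; 50:50 to 70:30 is assumed, with equal arms in each city and the same death rates in both.

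**1. The plan's own figure.** With pooled variance, two-sided 5% and 200 per arm, power for 17% vs 10% is 53.5%. For 80% power, 373 per arm would be needed. The plan states no power, so the 200 is not reproduced at a conventional level. That is a separate matter; it is relevant here because precision is limited even before any split by city.

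**2. Overall precision.** Variance term v = 0.17×0.83 + 0.10×0.90 = 0.2311. Half-width of the 95% interval = 1.96×√(0.2311/200) = 6.7 points.

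**3. Precision within a city.** Half-width = 1.96×√(v/n), with n patients per arm in that city.

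| Split | n per arm in each city | Half-width (points) |
|---|---|---|
| 50:50 | 100 and 100 | 9.4 and 9.4 |
| 70:30 | 140 and 60 | 8.0 and 12.2 |

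**4. Difference in effect between cities.** SE = √(SE₁² + SE₂²).
- 50:50: SE 6.8 points and half-width 13.3 points. Power for a 7-point difference in effect is about 18%. The difference detectable with 80% power is about 2.8×6.8 = 19 points.
- 70:30: SE 7.4 points, half-width 14.5 points, power about 16%.

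**5. Chance imbalance in city without stratification.** With 400 patients in two equal arms, the 95% range for the between-arm difference in Sheffield share is 1.96×√(p(1−p)×4/400). This is ±9.0 points at p = 0.3 and ±9.8 points at p = 0.5. As an illustration, suppose mortality differed by 5 points between the cities. A 10-point imbalance would then move the estimate by 0.10×5 = 0.5 points, against the overall half-width of 6.7. This is ordinary chance variation, not bias.

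**6. What a difference in usual care could do (illustration only).** Suppose Leeds supplies half the patients and its true effect is 3.5 points instead of 7. The average effect is 0.5×3.5 + 0.5×7 = 5.25 points, and two-sided power falls from 53.5% to 32%. If the effect is 7 points in both cities, nothing is lost. The documents do not say which applies.

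**The case against.** **The aim is not out of reach.** A reader might infer that regional variability cannot be studied at all. The documents do not support that. Address is collected and the regression covariates are open, so city could be analysed. The Sheffield sentence also stands before the study is divided into its two parts, and may refer to the characteristics of patients with severe hypoglycemia rather than to the treatment effect. This stands: the gap is that nothing is planned. Under either reading, however, the Statistical analysis section names no summary by city.

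**The comparator is not shown to differ.** A reader might infer that the pooled effect mixes two different contrasts. Sheffield's care is not described, the existing pathway may simply be extended there, and the standard-arm contact rule does not distinguish the cities. The carbohydrate-counting item, "Teach CHO counting (structured education with dietitian already in place", names no city. This stands: local protocols allow a difference but do not establish one.

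**Leeds controls are not shown to receive the email component.** The text says "An email system is already set up in Leeds by the PI" but not who may use it, and it lists the trial's line only for the intensive arm. Any figure for the share of controls exposed would be a product of assumptions. This stands.

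**The pooled comparison is valid.** It estimates the average effect over the two cities, and chance imbalance is covered by the test's error rate. This stands.

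**City results would be too imprecise to explain a null result, and two cities cannot separate region from centre.** This also stands, and it limits the remedy to description. It does not remove the case for the remedy, because description is what the stated purpose needs and it costs little.

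Finally, because the design figures are not available, the absence of randomisation by city can be asserted only of the visible text.

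**Conclusion.** The point holds in limited form. The protocol gives learning about regional differences as one of two reasons for adding Sheffield, and no planned step in randomisation or analysis serves it. This is an omission in planning, not a flaw in the validity of the main comparison.

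Its size is modest. City-specific mortality differences would carry 95% intervals of about ±8 to ±12 points, and power to detect a 7-point difference in effect between cities would be about 16 to 18%. These figures rest on assumed splits of 50:50 to 70:30, on equal arms within each city, and on 17% and 10% mortality applying in both cities although the 17% comes from Leeds alone. City findings would have to be labelled descriptive.

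**What to change.** 1. Randomise within city, using separate Leeds and Sheffield lists.
2. Stratify or adjust each comparison between arms by city: for example, Mantel-Haenszel for the 2×2 tables and a city term in models.
3. Report, for each city, baseline characteristics and the arm difference with its 95% interval, labelled descriptive in advance. This serves both readings of the stated purpose.
4. Describe usual care in each city briefly in the protocol, so that a reader can judge whether the comparators are alike.
5. Optionally, record use of the existing Leeds email service at enrolment in both arms. Do not add a later contact for this, because the standard arm is limited to one.

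**Cost.** A second allocation list, one stratum or model term, one extra table and, if taken up, one yes/no item at enrolment. No increase in sample size is needed. The downside is slightly more analysis, and city-specific estimates that are imprecise and must not be read as tests.

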### Observational study

Various details will be collected to elucidate the characteristics of patients undergoing severe hypoglycemia requiring emergency services intervention.

**Demographic and general data.** Address, age, sex, type of diabetes and duration, weight, body mass index, blood pressure, presence of macrovascular and microvascular complications, current treatment, status at home (living alone), driving status, alcohol consumption, smoking history, mobility, non-diabetes related co-morbidities. We will also clarify who made the ambulance call (patient/carer/other).

**Patient questionnaire (see appendix 1).** This will address whether a patient feels confident regarding managing his/her diabetes, how often glucose is monitored, can the patient adjust insulin, does the patient understand the dangers of hypoglycemia, presence of hypoglycemia awareness, frequency of low glucose levels, treatment options of hypoglycemia.

**Examination.** Check injection sites for lipoatrophy or lipohypertrophy and examine for signs of peripheral neuropathy (monofilament test).

**Blood and urine tests.** These will be arranged as part of routine clinical care in both groups, unless recent blood tests have been done. The following tests will be included: HbA1c, urea and electrolytes, liver function tests, full lipid profile, thyroid function tests (where appropriate), urinary albumin/creatinine ratio (ACR). HbA1c will be measured every 3 months, U&Es, LFTs and lipid profile 6 monthly. ACR will be checked at enrolment and at 12 months. All above tests will be requested more frequently if clinically indicated.

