**How often do you test your blood glucose (sugar) levels?**

1. At least twice a day with additional testing as needed.
2. At least once a day.
3. Less than once a day but at least twice a week.
4. Less than once a week.
5. Never.

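### Modifiable exposures (treatment, glucose testing, alcohol, home support) are recorded after the severe event with no pre-event reference period; a few event-anchored form fields would fix this cheaply.

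*Combined protocol and SAP*

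**What the plan says.** The first aim reads "Observational study: characterise individuals with severe hypoglycemia". The Observational study section says the data are to show the "characteristics of patients undergoing severe hypoglycemia requiring emergency services intervention", so the event comes before all data collection.

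The items at issue are these:

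- **Treatment and social items** (Observational study, demographic and general data): "current treatment, status at home (living alone), driving status, alcohol consumption, smoking history".
- **Medication record** (Interventional study): "The nurse will also document current medications with special attention to dose and frequency of hypoglycemic agents, including insulin".
- **Glucose testing** (Appendix 1): "How often do you test your blood glucose (sugar) levels", with answer categories but no recall period.
- **Timing** (Interventional study): "Patient will be asked to fill in the questionnaire at enrolment", then again at three months.

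The Hypothesis section states: "Inadequate education, infrequent glucose testing and clinical co-morbidities in subjects with diabetes are associated with severe hypoglycemic episodes". The Statistical analysis section plans a multiple regression to look for possible causes of hypoglycemia. It does not say whether the index event or later events are meant.

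**The concern.** The exposures that the plan wants to relate to severe hypoglycemia are ones that a severe event can itself change. After an ambulance call, a patient may start testing more often, drink less or get more help at home, and a care team may alter treatment. A form that asks only about the present then records the altered state.

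At stake is the description of cases under the first aim, together with any conclusion about what led to the index event. If infrequent testing is a candidate cause, the useful figure is how often patients tested before the call. A state not captured at enrolment becomes harder to recover later.

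**Working it through.** The plan gives no figure on this point. Its one calculated number, 200 per arm for mortality, is not an input here. The check sets the sections side by side.

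**1. Order in time.** Entry follows an ambulance-attended event. The questionnaire is first completed at enrolment. The readable text gives no interval from event to enrolment, no instruction to record the pre-event state, and no log of changes made in between.

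**2. Reference time of each item.**

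- Glucose-lowering treatment: labelled as current in both the Observational study and Interventional study sections.
- Testing frequency, checking when hypoglycemic, frequency of attacks, warning symptoms, insulin adjustment (Appendix 1): present tense, no recall period.
- Alcohol, living alone, driving (Observational study): undated.
- Assisted attacks (Appendix 1): past 12 months. This item has a look-back, but it counts events, not exposures.
- Who made the ambulance call: tied to the event.
- Age, sex, diabetes type and duration, established complications: barely altered by a short delay.

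The gap therefore covers the modifiable exposures only.

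**3. What the uses require.** The hypothesis links infrequent testing and inadequate education to severe episodes. The Background asks whether infrequent testing and poor clinical support raise the risk. The Interventional study section has the nurse look for the cause of the episode. Each of these needs the state before the event.

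**4. Is change before enrolment plausible?** The Background refers to existing local pathways meant to increase clinical support. The legend to the current pathway (Plan of investigation) names the diabetes nurse specialist and the GP. The Interventional study section foresees treatment changes after such an event, as a study action. It also encourages testing at least twice a day, which is the best category of the Appendix 1 item, so early advice of the same kind could move a patient straight into that category. None of this shows that change does happen before enrolment.

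**5. Size, on assumptions only.** Let P be the pre-event prevalence of an exposure and c the share of exposed patients who leave that category before enrolment, with nobody moving into it. The recorded prevalence is P × (1 − c). The documents give neither P for testing nor any c. With P assumed at 40%:

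- c = 10%: 0.40 × 0.90 = 36%
- c = 20%: 0.40 × 0.80 = 32%
- c = 30%: 0.40 × 0.70 = 28%
- c = 50%: 0.40 × 0.50 = 20%

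This shows how the mechanism works. It does not estimate what will happen in this study.

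**The case against.** The strongest case against has five parts.

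- **The aim is only to characterise patients.** It does not promise to reconstruct a pre-event state, and a question on how often one tests is naturally answered with usual habit. This stands in part. The aim is neutral, but the hypothesis and the nurse's search for the cause give it an explanatory purpose.
- **A remedy is already there.** The nurse takes a detailed history to find the cause, covering alcohol, independence and carer help, and such a history looks backwards. It helps but does not close the gap: it is undated, sits under the Interventional study and goes with a record of current medications. It is also unclear whether standard-arm patients, who have a single contact, receive it.
- **Change before enrolment is inferred.** This stands. The treatment changes described are study actions. The pathway, design and schedule figures are not readable, and the legend to Figure 4 defines a day unit, so an interval may be shown there.
- **Enrolment values may be the right ones.** If the regression concerns later hypoglycemia, they are the proper baseline. This stands, and is why they should be kept.
- **The look-back window is a choice.** No length follows from the documents, and any length brings recall error. This stands.

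A reader might also infer that late recording understates the link between these exposures and the index event. The documents do not support that. Everyone described has had the event and no event-free comparison group is described, so no such association is estimated. What can be distorted is the description of cases.

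**Conclusion.** The point holds as a cheap improvement. For treatment, testing frequency, alcohol and home support, the readable text sets no period before the event, and the information is collected after it. If these change before enrolment, the description of cases and any analysis of causes of the index event will reflect the changed state.

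The size is unknown. The conclusion rests on one assumption, that some patients or care teams act between the event and enrolment, which is plausible from the existing support pathway but neither documented nor quantified. A shift towards better habits is likely but is not shown either.

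A reader might go further and conclude that the first aim cannot describe the pre-event state at all, or that every item is recorded as current. Neither follows. Stable characteristics and the 12-month item are unaffected, and only treatment and medications carry the word current. Nor should the Background's 95% sulphonylurea use be turned into an expected loss for the whole cohort. It applies to the 28% of type 2 cases not on insulin, which is 0.28 × 0.95 = 26.6% of type 2 cases, and no rate of stopping before enrolment is given.

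**What to change.** - Record the date of the ambulance call and the date of enrolment.
- Add to the enrolment form the glucose-lowering drugs and doses in use at the time of the call, checked against GP or ambulance records where available.
- Add testing frequency, alcohol intake and home support for a stated short period before the call. Four weeks is one workable choice; the documents do not fix the length.
- State in the Statistical analysis section that these values are used to describe the characteristics or causes of the index event.
- Keep the present-tense items unchanged as the baseline for the three-month questionnaire comparison and for analyses of later hypoglycemia.

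The cost is a few extra fields, with no added visit. The downside is some recall error in the pre-event items, limited for drugs by the record check. Any percentages used to illustrate the problem should be labelled as assumptions or left out.

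### Repeated laboratory values such as HbA1c are to be compared by an unadjusted t-test or Mann-Whitney test, with no visit, summary or enrolment-value adjustment stated

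*Combined protocol and SAP*

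**What the plan says.** The Observational study section (blood and urine tests) gives the timing: "HbA1c will be measured every 3 months, U&Es, LFTs and lipid profile 6 monthly". It applies to both arms: "These will be arranged as part of routine clinical care in both groups, unless recent blood tests have been done". The Interventional study section carries this into the randomised part: "Blood tests will be arranged as detailed above".

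In that section the intensive arm's nurse contacts thin out after the first month: "every two weeks for the following month followed by contact at months 3, 6 and 12". No contact falls at month 9. The standard arm is contacted once, and its later care is left to the treating physician.

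The Statistical analysis section is one paragraph. For continuous data it says "Between group analysis will be done using unpaired" t-test if the data are normal, and otherwise "the non-parametric Mann-Whitney test will be used for data that are not normally distributed". The remaining methods are for other purposes: "For categorical data, 2X2 contingency tables will be used and multiple regression analysis will be performed to determine potential causes of hypoglycemia".

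The only outcome time in the readable text is in the caption of Figure 4: "Clinical outcome at 12 months will also include frequency of hypoglycemia, analysed separately". The statistical paragraph does not link any laboratory value to that time.

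**The concern.** Both named tests take one number per patient. The schedule yields up to four follow-up HbA1c values and two follow-up renal, liver and lipid values, plus a value at or near enrolment. The readable text does not say which number enters the test. That has three consequences.

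- The enrolment value, usually the strongest predictor of a later laboratory value, is not used.
- A patient with no value at the chosen visit drops out of the comparison, even if other follow-up values exist. Such gaps are likely where tests rely on routine care, where one arm is contacted only once, and where no month-9 contact is planned.
- With no visit fixed in advance, the analyst could test several visits or choose one after seeing the results.

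At stake are the precision and credibility of the arm comparison for the laboratory values. The mortality comparison that sets the sample size is not affected.

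**Working it through.** **The plan's own figure.** There is none on this point. The stated 200 per arm was derived for mortality. The documents give no standard deviation or correlation for HbA1c, so the within-patient correlation r is an assumption here, taken as 0.6 to 0.8 and equal between all visits.

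**Number of values.** 12 months / 3 months = 4 follow-up HbA1c values (months 3, 6, 9, 12). 12 / 6 = 2 for renal, liver and lipid tests.

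**If every HbA1c visit were tested at two-sided 5%.** The chance that at least one of four test statistics exceeds 1.96 in absolute value with no true effect:

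| Correlation | Chance of at least one false positive |
|---|---|
| independent | 1 - 0.95^4 = 18.5% |
| 0.6 | about 14.5% (simulation) |
| 0.7 | about 13.1% (simulation) |
| 0.8 | about 11.4% (simulation) |

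If correlation instead decays with time between visits, simulation gives 14.4% at 0.7 and 12.6% at 0.8, so the equal-correlation assumption is not critical.

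**Gain from the enrolment value at month 12, complete data.** The variance of the arm difference relative to an unadjusted t-test is 1 - r^2:

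- r = 0.6: 1 - 0.36 = 0.64
- r = 0.7: 1 - 0.49 = 0.51
- r = 0.8: 1 - 0.64 = 0.36

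In standard-deviation units, with 200 per arm all measured and 80% power, the unadjusted test detects (1.960 + 0.842) x sqrt(2/200) = 0.28. Multiplying by sqrt(1 - r^2) gives 0.28 x 0.80 = 0.22 at r = 0.6 and 0.28 x 0.60 = 0.17 at r = 0.8. All 200 will not be measured. On the planning rates of at least 17% and 10%, about 0.17 x 200 = 34 and 0.10 x 200 = 20 patients die within the year, leaving at most 166 and 180.

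**What the repeated values add.** With complete data, the month-12 estimate from a mixed model is essentially no more precise than a month-12 comparison adjusted for enrolment. The gain appears when month-12 values are missing, because earlier values then carry information about them.

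**Averaging over follow-up instead.** Against an enrolment-adjusted single visit, the variance ratio for the mean of four values is [(1 + 3r)/4 - r^2] / (1 - r^2):

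- r = 0.6: (0.70 - 0.36)/0.64 = 0.531
- r = 0.8: (0.85 - 0.64)/0.36 = 0.583

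The reciprocals, 1.9 and 1.7, are equivalent multiples of the sample size. They require four complete values and the same arm effect at every visit. If the effect builds linearly to month 12, the mean effect is (0.25 + 0.50 + 0.75 + 1)/4 = 0.625 of the month-12 effect. Relative efficiency is then 0.625^2/0.531 = 0.74 down to 0.625^2/0.583 = 0.67, which is a loss.

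**The case against.** The strongest reply is that the plan never says it will test visit by visit or use only one visit. A t-test on each patient's mean follow-up value is a single test, uses every value, and has variance (1 + 3r)/4, which is 0.70 to 0.85 of a single-visit test. This is right. A reader might infer that the plan must either test four visits or discard most of the data; the text does not support that, because a per-patient summary is a third route. But no such summary is defined, and it would still ignore the enrolment value.

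Figure 4 is also missing from the readable text, and its abbreviation list suggests that it shows laboratory tests and times. It may fix a visit. That would answer the multiplicity part, but not the unused enrolment value or the patients who missed that visit.

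A reader might further infer that HbA1c is the plan's safeguard against fewer attacks being bought with worse control. No section says so. The Aims name hypoglycemic events, confidence and quality of life, and clinical outcome, and the sample size rests on mortality. The point therefore concerns a supporting measure in a study that calls itself preliminary.

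Finally, a reader might quote a gain equivalent to 1.7 to 1.9 times as many patients. That is a best case for an average contrast, and the documents' own follow-up arrangements and expected mortality make it unlikely.

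**Conclusion.** The point holds as an inexpensive improvement to the analysis of a secondary set of measures, not as a flaw in the main comparison. The plan collects repeated laboratory values in both arms, but the readable text names only tests that take one unadjusted value per patient and does not say which value.

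The supportable size is a variance of about 0.64 to 0.36 of that of an unadjusted month-12 t-test. This assumes complete data and a correlation of 0.6 to 0.8, and comes mainly from the enrolment value. The false-positive figure of about 11% to 15% is conditional on all four HbA1c visits being tested at 5%, which the plan does not state. The benefit of the repeated values depends on how many month-12 values are missing, which the documents do not allow one to predict.

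**What to change.** For each repeatedly measured laboratory outcome, replace the t-test with a linear mixed model containing arm, visit, arm-by-visit and the enrolment value, fitted to all available follow-up values. Name the month-12 arm difference as the single test, in line with the outcome time in the Figure 4 caption. Show the other visits and the follow-up average as description. Where values are skewed, state the transformation in advance. Because recent tests may stand in for new ones and extra tests may be requested, define which result counts as the enrolment value and what window each visit covers.

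The cost is a short paragraph in the Statistical analysis section, with no new patients, visits or measurements. There are two downsides. The model assumes that missing values are missing at random given the observed ones. It also does not resolve values that do not exist because the patient died, so deaths and the number of available values at each visit should be reported by arm. Choosing month 12 over the average gives up precision if the effect is constant, but avoids diluting an effect that builds over the year.
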